### **Second-dose Safety**

Post-second dose 48-hour and 7-day safety assessments will be monitored by the PI(s) and the SRP(s). Administration of the second dose will also be staggered to allow safety assessments to be made 7 days after the second dose in all 12 adults in Cohort 0 before administering the second dose to seropositive toddlers in Cohort 1. Likewise, safety assessments will be made 7 days after the second dose in the first 12 seropositive toddlers in Cohort 1 before administering the second dose to the remaining seropositive toddlers in Cohort 1. In addition, 48-hour safety will be

checked after dosing sentinel subjects in both cohorts. Safety data for review will include solicited and unsolicited AEs and SAEs. In the absence of clinically relevant findings, enrollment and dosing for the next cohort of subjects will continue as described above.

[figure not shown]
The sponsor will monitor post-vaccination safety on an ongoing basis by reviewing blinded safety data.

**Table 5: Study Design**

Cohort	Group	N	Day 1	Day 29/Week 4
ADULTS 18 to 50 years				
0	Group 1	8	Ad26.RSV.preF ( $1 \times 10^{11}$ vp)	Ad26.RSV.preF ( $1 \times 10^{11}$ vp)
	Group 2	4	Placebo	Placebo
TODDLERS 12 to 24 months: RSV seropositive				
1	Group 3	24	Ad26.RSV.preF ( $5 \times 10^{10}$ vp)	Ad26.RSV.preF ( $5 \times 10^{10}$ vp)
	Group 4	12	Placebo	Placebo

**Figure 1: Enrollment and First Dose Strategy**

\*Two Cohort 0 sentinel subjects, and the parent/legal guardian of 2 sentinel subjects from Cohort 1 will be contacted on Day 3 by telephone to collect safety information.

After each vaccination, all subjects will be closely observed for a minimum of 30 minutes post-vaccination, or a minimum of 60 minutes post-vaccination according to local approvals, to monitor for the development of any acute reactions, or longer if deemed necessary by the investigator. Any unsolicited, solicited local or systemic AEs and vital signs will be documented by study-site personnel following this observation period. Subjectsa will be given a thermometer, ruler and daily assessment (subject) diary with instructions for the proper recording of events. Each subject will record solicited local (at injection site) and systemic AEs and body temperatures, beginning on the evening of each study vaccine dosing day and on a daily basis for the following 7 days. Temperaturesb should be taken at approximately the same time each day, preferably in the eveningc and, for pediatric subjects, additionally whenever the child feels warm. Study-site personnel will collect and review subject diary information and confirm the entries at subsequent site visits.

Unsolicited AEs will be collected from the time of informed consent through 28 days after each dose. For both cohorts, all SAEs will be collected from ICF signature to the end of the study. All AEs, including any that are ongoing at 28 days after each dose, will be followed until clinical resolution or stabilization. Concomitant medications will be collected from the time of each vaccination through 28 days after each vaccination, and additionally outside of these periods when associated with any SAE.

Blood will be collected for immunogenicity assessments as follows:

- Cohort 0: pre-vaccination for first and second doses, and at 28 days and 6 months after the second dose
- Cohort 1: pre-vaccination for first and second doses, and at 28 days and 6 months after the second dose

For Cohort 1, a blood sample will be taken for RSV serology at screeningd; the baseline sample for immunogenicity may either be drawn at the same screening visit or pre-dose on Day 1, at the discretion of the investigator.

Unscheduled study visits may be performed based on investigator's clinical judgment and may include further evaluations, as needed.

Diagrams of the entire study design by cohort are provided in [Figure 2](#) (Cohort 0) and [Figure 3](#) (Cohort 1).

---

[figure not shown]
a In Cohort 1, activities to be performed by the subject refers to the parent/legal guardian.

[figure not shown]
b Recommended orally for adult subjects; rectally or axillary for pediatric subjects (actual routes to be recorded in the eCRF).

c All Day 8 post-vaccination diary assessments, including temperature measurements, may be collected earlier to coincide with the corresponding clinic visit.

d 0.5 mL of blood for serostatus assessment can be collected by venous blood sample or fingerstick, at the discretion of the investigator. If 0.5 mL is collected at screening, baseline blood draw for immunogenicity should be on Day 1.

**Figure 2: Schematic Overview of the Study for Cohort 0**

**Figure 3: Schematic Overview of the Study for Cohort 1**

\*If Visit 9 occurs during the RSV season, an additional visit will be made by telephone at the end of the RSV season to collect safety information

### Safety Follow-up

Parent(s)/legal guardian(s) of subjects in Cohort 1 will be contacted by telephone (or clinic visit) through 1 year after the first dose (including during the active phase and safety follow-up phase: every 30 days  $\pm$  7 days outside the RSV season, but every 14 days  $\pm$  3 days in season). During each 28-day post-vaccination period, calls will remind parents/legal guardians to contact the site in the event their child develops an RTI. During the RSV season, but outside the 28-day post-vaccination period, calls will remind parents/legal guardians to contact the site in the event their child develops a combination of symptoms of respiratory infection (persistent [ $>48$  hours] clinical symptoms of rhinitis [sneezing or runny nose or congestion] and persistence [ $>24$  hours] of one or more of the following: cough, abnormal breathing, fever, lethargy or decreased

appetite). These calls will also check for any SAEs and associated concomitant medications since the previous visit or telephone contact.

### 3.2. RTI – Procedures Specific to Cohort 1

Monitoring of RTIs will take place during each 28-day post-vaccination period, and additionally during the RSV season after the first dose (even if it falls outside of the 28-day post-vaccination period). Monitoring for MA-RTIs and severe LRTIs will take place during the whole study period.

During each 28-day post-vaccination period, all RTIs will be reported, nasal turbinate samples will be collected as soon as possible after the onset of respiratory symptoms, and signs and symptoms will be recorded by the attending health care professional using the RTI Symptoms Form.

If, during the RSV season, but outside the 28-day post-vaccination period, a subject shows persistent (>48 hours) clinical symptoms of rhinitis (sneezing or runny nose or congestion) and persistence (>24 hours) of one or more of the following: cough, abnormal breathing, fever, lethargy or decreased appetite, the study site should be notified. Nasal turbinate samples will be collected as soon as possible after the onset of these combined respiratory symptomsa. When nasal turbinate samples are collected, the attending health care professional will record signs and symptoms of the RTI using the RTI Symptoms Form.

Nasal turbinate samples will not be collected if less than 7 days after the previous sample collection.

Outside of the RSV season, nasal turbinate samples will only be collected from subjects with MA-RTIs or severe LRTIs (for definition of MA-RTI and severe LRTI, please refer to Section 11.3.1).

Throughout the study, nasal turbinate samples will be collected from any subject with a MA-RTI or severe LRTI.

The criteria used to assess potential cases of RSV infection in subjects from Cohort 1 will be as follows:

- Suspected RSV infection: subject has persistent (>48 hours) clinical symptoms of rhinitis (sneezing or runny nose or congestion) and persistence (>24 hours) of one or more of the following: cough, abnormal breathing, fever, lethargy or decreased appetite.

Occurrence of this combination of symptoms in any subject would trigger collection of a nasal turbinate sample.

---

a These procedures should preferentially be performed at the study site. These procedures can be conducted at the subject's home by site staff or qualified professional staff if the study site has an established standard operating procedure as such. In case of emergency, the procedures can be done in a hospital.

- Confirmed RSV infection: subject with suspected RSV infection and positive for RSV on the basis of RT-PCR conducted centrally.

Data on the clinical course of infection including information regarding oxygenation status, supplemental oxygen requirements and specific drug treatments should be collected, as well as any other concurrent respiratory illness present at the time of the diagnosis of the event and up to symptom resolution.

To ensure the rapid follow-up of any severe LRTI or MA-RTI, study sites will need to make arrangements with primary care physicians, emergency departments and/or hospitals' urgent care facilities to be notified when a subject is being seen. Further details will be provided in the Trial Center File. Any parent/legal guardian who seeks medical attention for their child due to an RTI should make the attending health care professional aware that their child is taking part in an RSV vaccine study. Each child's parent/legal guardian will be given a wallet card with key study information and site contact details (see Section 12.3.1). These details should be shared with the attending health care professional.

*Note:* Any RTI falling within the 28-day post-vaccination period will be reported as an unsolicited AE, preferably as a diagnosis. Any RTI fulfilling the criteria of an SAE would be reported as such during the entire study. Any severe LRTI will be reported using the SAE reporting system and SAE form, regardless of whether the event fulfills the criteria of an SAE.

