- r. Subjects will be closely observed for a minimum of 30 minutes post-vaccination, or a minimum of 60 minutes post-vaccination according to local approvals. Any unsolicited, solicited local and systemic AEs, and vital signs will be documented by study-site personnel following this observation period
- s. Concomitant medications will be collected from the time of each vaccination through 28 days after each vaccination, and additionally outside of these periods when associated with any SAE. Pre-study therapies administered up to 30 days before first dose of study vaccine will be recorded during screening
- t. Monitoring of RTIs will take place during each 28-day post-vaccination period, and additionally during the RSV season after the first dose (even if it falls outside of the 28-day post-vaccination period). During each 28-day post-vaccination period, nasal turbinate samples will be collected for all RTIs. If, during the RSV season, but outside the 28-day post-vaccination period, a subject shows persistent (>48 hours) clinical symptoms of rhinitis (sneezing or runny nose or congestion) and persistence (>24 hours) of one or more of the following: cough, abnormal breathing, fever, lethargy or decreased appetite, the study site should be informed and nasal turbinate samples will be collected for these subjects. Note: Nasal turbinate samples will not be collected if less than 7 days after the previous sample collection
- u. When nasal turbinate samples are collected, the attending health care professional will record signs and symptoms of the RTI using the RTI Symptoms Form
- v. At Visit 2, rulers and thermometers will be distributed to subjects in Cohort 0, and to parent(s)/legal guardian(s) of subjects in Cohort 1
- w. At least 5 toddlers in the active group are to have received first dose in a clinic setting and to have completed Visit 3 with no safety concerns before moving to vaccination of study subjects in a non-clinic setting (safety information of the first 5 active toddlers will be monitored by the PI(s)/SRP(s) through Visit 3, and escalated to the IDMC in the event of a safety signal).
- x. Blood draw for serology testing will not exceed 15mL

Note: Body temperatures for Cohort 0 recommended to be measured orally; body temperatures for Cohort 1 recommended to be measured either rectally or axillary (actual routes to be recorded in the eCRF)

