### **9.2.2. Other Evaluations – RSV Infection**

RSV seropositivity of Cohort 1 subjects will be assessed by RSV EIA or virus neutralization assay at screening. The cut-off for seropositivity by EIA is a titer >10 EIA units and the cut-off by virus neutralization assay is a titer >4. *Note:* RSV-seropositive toddlers may be recruited if RSV seropositivity was assessed via either of these assays in a different study of the sponsor.

Nasal turbinate samples, taken from any Cohort 1 subject with an RTI during each 28-day post-vaccination period, and from any Cohort 1 subject with a combination of respiratory symptomsa during the RSV season (but outside of the 28-day post-vaccination period), and from any Cohort 1 subject with a MA-RTI or severe LRTI during the whole study period, will be assessed for the presence of RSV infection by RT-PCR. The actual dates and times of sample collection must be recorded in the eCRF or laboratory requisition form.

a Persistent (>48 hours) clinical symptoms of rhinitis (sneezing or runny nose or congestion) and persistence (>24 hours) of one or more of the following: cough, abnormal breathing, fever, lethargy or decreased appetite.

In addition, scheduled blood samples may be assessed for the presence of RSV antibodies by serology.

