### 11.3. Criteria for Exploratory Endpoints

#### 11.3.1. Definitions for Exploratory Endpoints

The exploratory endpoints shown below will be collected to assess the feasibility of, and gain expertise in the collection of such events for future studies.

- RSV MA-RTI: All subjects with RSV-RTI that is medically attended, ie when the subject's parent/legal guardian seeks medical attention outside of normal study procedures, including health care professional's visit to the home, clinic visit, emergency room attendance, and hospital admission. (*Note*: medical attention outside normal study procedures will as much as possible also be captured on the RSV Symptoms Form.)
- Severe LRTI: For subjects in Cohort 1, severe RSV-LRTI will be defined as the presence of severe LRTI as assessed by the CEC, and a positive assessment for RSV.

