##### 11.3.1.2. Determination of RSV Positivity

- A subject is considered RSV positive if he/she has a positive RT-PCR for RSV on nasal turbinate samples (central laboratory).

- If a RT-PCR test result for RSV is missing (ie, not available or not conclusive), the CEC will assess RSV positivity using all available clinical and laboratory information.

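### The 7-day limit on repeat nasal sampling conflicts with the promise to sample every MA-RTI and severe LRTI, and Section 11.3.1.2 does not say whether an earlier negative swab settles RSV status

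*Protocol*

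**What the plan says.** **Sampling.** The Protocol Synopsis (RTI procedures for Cohort 1) and Section 3.2 give the limit as a paragraph of its own: "Nasal turbinate samples will not be collected if less than 7 days after the previous sample collection". Two short paragraphs later comes the promise: "Throughout the study, nasal turbinate samples will be collected from any subject with a MA-RTI or severe LRTI". Section 9.2.2 builds the virology on that promise, with RT-PCR testing of the samples taken from these toddlers at any point in the study. The Cohort 1 Time and Events Schedule repeats the limit inside footnote t: "Note: Nasal turbinate samples will not be collected if less than 7 days after the previous sample collection".

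**Timing of the first swab.** In each 28-day post-vaccination period every RTI is sampled: "nasal turbinate samples will be collected as soon as possible after the onset of respiratory symptoms". In the RSV season outside those periods, the trigger is rhinitis lasting more than 48 hours plus another listed symptom lasting more than 24 hours. Outside both, only MA-RTIs and severe LRTIs are sampled.

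**Classification.** Under Section 11.3.1, "severe RSV-LRTI will be defined as the presence of severe LRTI as assessed by the CEC, and a positive assessment for RSV". Section 11.3.1.2 makes a subject RSV positive on a positive central RT-PCR, and adds a fallback: "If a RT-PCR test result for RSV is missing (ie, not available or not conclusive), the CEC will assess RSV positivity", using all clinical and laboratory information. Separately, Section 3.2 and SAP Section 7 define a confirmed RSV infection as a suspected one with a positive central RT-PCR. Under Protocol Section 11.9.1 the CEC outcome and the RSV determination both go to the IDMC.

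**The concern.** The two sampling rules give opposite instructions for the same child. If an RTI is swabbed at a mild stage and becomes medically attended or severe less than 7 days later, one rule forbids a sample and the other requires it. A site cannot tell from the text which to follow.

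If the site follows the limit, there is no virology from the severe stage. RSV status then depends on how Section 11.3.1.2 is read, and that section links no swab to any episode. If the early swab was a false negative, or the child acquired RSV a few days after a cold from another virus, a true severe RSV-LRTI could drop out of the count.

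Monitoring for severe RSV-LRTI is a stated exploratory objective (Section 2.1.1) and one of the listed safety measures (Section 3.4.5). With 24 vaccinees and 12 placebo recipients, the count is likely to be zero or very small, and one case changes what is reported.

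**Working it through.** No stated figure depends on this point, so the check is mainly textual.

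**Step 1: when the rules collide.** Suppose a swab is taken on day *d* of an illness and the illness becomes an MA-RTI or severe LRTI on day *d + k*.

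- *k* of 7 or more: no conflict.
- *k* below 7: the limit says no sample and the promise says sample. Neither has an exception.

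**Step 2: when *k* below 7 can arise.**

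- In the two 28-day windows (target Days 1 to 29 and 29 to 57, so 28 + 28 = 56 days), every RTI is swabbed soon after onset. An early swab followed by worsening is the expected order of events.
- In season outside those windows, the symptom trigger delays the first swab, so the sequence is possible but less likely.
- Out of season and outside the windows, no routine mild-stage swab exists to start the 7-day clock.

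**Step 3: what follows for RSV status.** If the first swab was positive, the subject is already RSV positive and nothing is lost. If it was negative:

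| Site follows | Reading of Section 11.3.1.2 | Severe RSV-LRTI endpoint | Confirmed RSV infection (3.2, SAP 7) |
|---|---|---|---|
| The promise | Either | Decided by the new RT-PCR, or by the CEC if inconclusive | Decided by the new RT-PCR |
| The 7-day limit | Early negative is the subject's result | Not counted as RSV | Unconfirmed |
| The 7-day limit | Severe episode has no result of its own | CEC decides | Unconfirmed |

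The two lower rows assume no later positive sample. The limit lapses at 7 days, so a late swab is possible. The text supports neither reading of Section 11.3.1.2 over the other: it is worded by subject, and it does not say to which illness the result must belong.

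**Step 4: whether serology closes the gap.** Section 2.1.2 offers serology as a route to RSV infection only where no RT-PCR is available, which raises the same question. Section 9.2.1 also permits G or N serology in addition to RT-PCR, but as an option.

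**Step 5: scale, on assumed values only.** The documents give neither a severe RSV-LRTI rate nor the share of cases affected. The sample-size table in Section 11.2 uses 1 − (1 − p)^N. For N = 24 this gives 45.5%, 70.8% and 92.0% at rates of 2.5%, 5% and 10%, matching the printed 46%, 71% and 92%. Let p be an assumed true severe RSV-LRTI rate and m an assumed share of true cases counted as not RSV. With independent subjects, the chance of at least one counted case among 24 vaccinees is 1 − (1 − p(1 − m))^24:

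| p | m = 0 | m = 10% | m = 25% | m = 50% |
|---|---|---|---|---|
| 2.5% | 45.5% | 42.1% | 36.5% | 26.1% |
| 5% | 70.8% | 66.9% | 60.0% | 45.5% |
| 10% | 92.0% | 89.6% | 84.6% | 70.8% |

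These figures show sensitivity. They do not estimate what will happen.

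**The case against.** The strongest reply is that the documents never say such a child is RSV-negative. A reader might infer that the early negative swab fixes the classification and that the CEC fallback is then shut off. The text does not support that. Section 11.3.1.2 states when a subject is positive and has no negative rule. An unsampled severe episode can fairly be read as having no RT-PCR available, in which case the CEC decides. This stands: misclassification is a risk from an undefined link between swab and episode, not a stated outcome.

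Second, the limit might be meant only for routine swabs. Footnote t attaches to the RTIs row, while severe LRTIs and MA-RTIs have their own row without it. This weakens the schedule as evidence. It does not dispose of the Synopsis and Section 3.2, where the limit is a standalone, unqualified paragraph. One could also argue that a swab from the same illness already meets the promise, but no text says so.

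Third, a reader might infer that a severe case would vanish from safety monitoring. It would not. The IDMC monitors severe LRTI itself (Section 11.9.1), every severe LRTI goes on the SAE form, and all SAEs are collected to study end. Nor is the severe RSV-LRTI count the only information bearing on enhanced disease.

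Fourth, footnote u ties the symptoms form to sampling: "When nasal turbinate samples are collected, the attending health care professional will record signs and symptoms of the RTI using the RTI Symptoms Form". A reader might infer that the severe stage goes undocumented if no swab is taken. Section 3.2 asks for clinical-course data, including oxygenation, until symptoms resolve, and the CEC reviews SAE-form information. What may be lost is virology.

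Finally, the endpoint is exploratory, descriptive and collected for feasibility. That limits the weight of the point but does not justify contradictory sampling instructions.

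**Conclusion.** The conflict between the sampling rules is real and rests on the wording alone. The consequence is conditional. It needs a first swab that is negative, worsening to an MA-RTI or severe LRTI within 7 days, and a site that follows the limit. For the severe RSV-LRTI endpoint it also needs the early negative to be taken as that episode's result. Under the confirmed-infection definition, the case stays unconfirmed on either reading unless a later sample is positive. SAP Section 7 produces its suspected and confirmed summary only if a severe LRTI has occurred in Cohort 1, which is when the gap would matter.

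The number of children affected cannot be derived and is probably small among 36 seropositive toddlers. A correction is worthwhile because one case can alter an endpoint reported to the IDMC. The documents do not support saying that such a child is classed RSV-negative, only that this could happen.

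**What to change.** 1. **Sampling.** In the Synopsis, Section 3.2 and schedule footnote t, reconcile the text so that the 7-day limit governs routine repeat sampling and does not override the sampling of an MA-RTI or severe LRTI that the Protocol already promises.
2. **Classification.** In Section 11.3.1.2, state that when the only RT-PCR result is negative and predates the onset of the severe LRTI, it is treated as not available for that episode, and the CEC assesses RSV positivity from all information. State also that an earlier positive result stands. Without that limit, the rule would replace an objective positive with adjudication.

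The confirmed-infection definition can stay as it is, because the promised swab supplies the result it needs. The cost is a few sentences, an occasional repeat swab in a toddler and slightly more work for the CEC.

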### Exploratory Endpoints – RSV Infection

- For Cohort 1 only, RSV infection confirmed by either reverse transcriptase polymerase chain reaction (RT-PCR), or by serology for, but not limited to, protein G and/or N if no RT-PCR is available. To detect asymptomatic RSV infections, a fold increase will be applied to call a subject seropositive to G and/or N ELISA (or F in case of placebo subjects). Fold increases for RSV infection will be determined based on the (suspected) infection and the convalescent blood samples.
- In Cohort 1 throughout the study:
  - Severe RSV-LRTI
  - RSV medically-attended respiratory tract infection (MA-RTI)

Refer to Section 9.2 for evaluations related to endpoints.

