#### **11.6. RSV Infection**

Incidence of any RSV infection, as described in Section 3.2, in Ad26.RSV.preF and placebo subjects will be summarized by descriptive statistics.

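### Section 3.2 and SAP Section 7 confirm an RSV infection only if a symptom combination accompanies a positive RT-PCR, so PCR-positive toddlers swabbed by other routes can drop out of the infection rate

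*Protocol*

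**What the plan says.** Protocol Section 3.2 (repeated in the synopsis) sets up two categories for Cohort 1. The first is a symptom definition: "Suspected RSV infection: subject has persistent (>48 hours) clinical symptoms of rhinitis (sneezing or runny nose or congestion) and persistence (>24 hours") of at least one of cough, abnormal breathing, fever, lethargy or reduced appetite. The second builds on it: "Confirmed RSV infection: subject with suspected RSV infection and positive for RSV on the basis of RT-PCR conducted centrally". SAP Section 7 uses the same two categories, split into severe and non-severe. Section 11.6 promises "Incidence of any RSV infection, as described in Section 3.2", by vaccine and placebo.

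The sampling rules are wider than the symptom definition. Within 28 days of each dose, "all RTIs will be reported, nasal turbinate samples will be collected as soon as possible after the onset of respiratory symptoms". Separately, "Throughout the study, nasal turbinate samples will be collected from any subject with a MA-RTI or severe LRTI". Section 9.2.2 sends swabs from all of these routes to RT-PCR.

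Two other places define infection without symptoms. The exploratory endpoint in Section 2.1.2 is "RSV infection confirmed by either reverse transcriptase polymerase chain reaction (RT-PCR"), or by serology where there is no RT-PCR, and it aims to pick up asymptomatic infections as well. Section 11.3.1.2 states: "A subject is considered RSV positive if he/she has a positive RT-PCR for RSV on nasal turbinate samples (central laboratory"). If the RT-PCR result is missing or inconclusive, the clinical endpoint committee (CEC) decides.

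**The concern.** An exploratory objective is to assess RSV infection rates in vaccine and placebo toddlers. The sampling scheme finds infections by several routes, only one of which needs the rhinitis-plus-symptom combination. The category that is counted needs the combination every time. A child can therefore be RSV positive by the central laboratory and still be neither suspected nor confirmed, and no third category exists.

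Two things are at stake. The reported incidence may leave out infections that the trial has already detected. And the infection summary may disagree with the severe RSV lower respiratory tract infection (LRTI) endpoint about the same child, in a programme whose main safety worry is enhanced RSV disease.

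**Working it through.** The documents give no RSV attack rate, expected event count or share of positives meeting the combination. There is no planned figure to reproduce, so the check is one of logic followed by the size of one omitted child.

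**Step 1: which swab routes need the combination?**

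- Any respiratory tract infection (RTI) within 28 days of a dose: no. With two doses this covers 2 × 28 = 56 days.
- RSV season, outside those windows: yes.
- Medically attended RTI (MA-RTI) or severe LRTI at any time: no.

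**Step 2: apply each rule to four hypothetical PCR-positive toddlers.**

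| Child | Sections 2.1.2 and 11.3.1.2 | Section 3.2 and SAP Section 7 |
|---|---|---|
| A. RTI in the post-dose window, rhinitis for 36 hours, then well | Infected | Neither category |
| B. MA-RTI with cough and fever, no rhinitis | Infected | Neither category |
| C. Cough, fast breathing and chest indrawing, rhinitis never beyond 48 hours | Infected; severe RSV-LRTI if the CEC agrees | Neither category |
| D. Swabbed on the first day, later meets both durations | Infected | Confirmed, if the later course is used |

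Child C is possible because the severe LRTI criteria in Sections 11.3.1.1 and 11.9.2 include no rhinitis and no symptom duration. SAP Section 7 produces its summary only when a severe LRTI has occurred, so child C could trigger a table and not appear in it.

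**Step 3: size per child.** Table 5 of the protocol plans 24 vaccine and 12 placebo toddlers.

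- Vaccine: 1/24 = 4.2 percentage points.
- Placebo: 1/12 = 8.3 percentage points.

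**Step 4: how many children?** This needs assumptions. Let r be the share of the 36 toddlers who are PCR positive and s the share of positives who meet the combination. The expected number left out is 36 × r × (1 − s). The chance that at least one is left out is 1 − (1 − r(1 − s))^36.

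- r = 10%, s = 90%: 36 × 0.10 × 0.10 = 0.4 children; chance of at least one, 30%.
- r = 25%, s = 70%: 36 × 0.25 × 0.30 = 2.7 children; chance 94%.
- r = 50%, s = 50%: 36 × 0.50 × 0.50 = 9.0 children; chance close to 100%.
- s = 100% at any r: none.

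These values are illustrative. They show only that the answer depends on two quantities that the plan does not give.

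**The case against.** The best defence is that the documents conflict and do not set a rule to discard positives. The endpoint in Section 2.1.2 counts RT-PCR positives without symptoms, Section 11.6 speaks of any infection, and Section 3.2 also describes every sampling route. Section 3.4.5 even seems to use the word suspected more loosely inside the 28-day windows. A sensible analyst might count all positives. That is fair, but the only category in Section 3.2 or SAP Section 7 that uses RT-PCR is the narrow one, and a programmer following it literally would leave children A to C out.

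Four stronger readings are tempting, and the documents do not support them.

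- *Severe RSV-LRTI cases are lost to the trial.* They are not. That endpoint needs CEC adjudication and a positive RSV assessment, with no rhinitis condition. The case still reaches the independent data monitoring committee and the serious adverse event system. The MA-RTI definition likewise sets no rhinitis condition. What can go wrong is the incidence and a cell of the SAP Section 7 summary.
- *The per-protocol immunogenicity rule is defective.* It removes samples taken after natural infection on RT-PCR or other evidence, and it does not use the confirmed category. That is its intended handling.
- *Every positive swabbed early is excluded.* Nothing fixes suspected status at the time of the swab, and Section 3.2 collects the clinical course until symptoms resolve. Only children who never meet the combination are affected.
- *The vaccine will look better than it is.* That would need vaccination to shorten or soften symptoms, which neither document shows.

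**Conclusion.** The point holds as an inconsistency with a practical consequence. Read literally, Section 11.6 and SAP Section 7 can omit a centrally confirmed RSV positive from the infection incidence, including a child adjudicated as severe RSV-LRTI, while Sections 2.1.2 and 11.3.1.2 count the same child.

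The size is 4.2 points per omitted child in the vaccine arm and 8.3 in placebo, assuming the planned 24 and 12 are the denominators. The number of such children is unknown and could be zero. The direction of any bias is not established. The endpoint is exploratory and descriptive, so no hypothesis, error rate or power is touched. It is a modest point, worth correcting because the correction is cheap and the arms are small.

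**What to change.** In the synopsis, Section 3.2, Section 11.6 and SAP Section 7:

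- Count as a confirmed RSV infection any nasal sample positive by central RT-PCR, whatever triggered the swab.
- Keep the Section 2.1.2 serology route where no RT-PCR is available, and the Section 11.3.1.2 CEC assessment where RT-PCR is missing or inconclusive. A PCR-only flag would lose infections that the protocol now counts.
- Add a sub-row for whether the suspected-infection symptom criteria were met (yes or no), so the narrower count stays visible.
- Keep the symptom combination as a sampling trigger.

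Leave the per-protocol immunogenicity rule and the severe RSV-LRTI and MA-RTI definitions as they are.

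The cost is wording in those four places and one extra row in the table. No new samples or tests are needed: the RTI Symptoms Form is completed with each swab, and the clinical course is already collected. One limit remains. In season but outside the 28-day windows, a milder illness that is not medically attended is never swabbed, so selection on symptoms there happens before RT-PCR and this change does not remove it.
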